### 4.2 STUDY DESIGN AND SCOPE

This study is a post-market clinical follow-up study designed as a prospective, blinded-subject, blinded-evaluator, observational, multi-center evaluation of the Infinity DBS system. The clinical study will be conducted in up to 60 centers from the European Union, United States, Latin America, and Australia.

The clinical investigation has been designed to involve as little pain, discomfort, fear, and any other foreseeable risk as possible for subjects. Refer to the Risks Analysis section of this clinical investigation plan for details.

## Clinical Investigational Plan

Subjects who currently have an Infinity DBS system or have been recommended by the investigator for implantation of a DBS system and meet the standard requirements will be approached to participate in the study. Each subject will be screened according to the inclusion/exclusion criteria. If the subject meets all of the study inclusion criteria and none of the exclusion criteria, the subject will be informed about the study to determine if the subject is interested in participating. Baseline data may be collected from the subject's medical record. After the subject signs the informed consent and is enrolled in the study, the subject will undergo an Infinity DBS system implant if the Infinity DBS system is not already implanted.

During the surgery, the leads will be implanted according to the physician's standard operating procedures. The neurosurgeon will be instructed to implant the hourglass-shaped radiopaque marker facing posterior or toward the implanter during insertion (toward the back of the subject's head) so that contact/segments are easily identifiable. The orientation of the contacts will be collected. In addition, neurosurgeons will be instructed to plan placement to target between contacts 2 and 3. A pre-operative and post-operative image (Magnetic Resonance Imaging (MRI) or Computerized Tomography (CT)) will be obtained to assist with lead location data. The IPG will be activated according to the site's standard of care and will be programmed by trained personnel using the Clinician Programmer. The subject may be given a Patient Controller, dependent on the physician's recommendation for patient care. Subjects will return for evaluation 3, 6, and 12 months post-initial programming for follow-up visits. An optional long-term follow-up will collect additional information 24 months after initial programming, optionally by telephone, and at a 36-month follow-up visit. This study is for data collection purposes and there are no additional risks to patients who participate in this study other than those risks of having a deep brain stimulation system implanted.

A comparison of the therapeutic window using directional stimulation to the therapeutic window using omnidirectional stimulation will be performed for each lead on each subject. Subjects will be considered to have a greater therapeutic window with direction stimulation if one or both leads has a larger therapeutic window with directional stimulation than omnidirectional stimulation.

A blinded evaluator will be used in this study to minimize study bias. The blinded evaluator will assess the therapeutic window for each subject at initial programming, the 3-month visit and the 12-month visit. The UPDRS part III motor examination for each subject will also be assessed by the blinded evaluator at the 3-month and 6-month visits. The blinded evaluator will not be aware of the subject's programming or device settings at the time of the evaluation. In addition, subjects will be unaware of their programmed parameters for the first 6 months.

All serious adverse events (SAEs), serious procedure-related events (and procedure-related AEs lasting longer than 30 days) and device-related adverse events will be recorded throughout the subject's participation in the study.

### 4.2.1 Number of subjects required to be included in the study

Up to 350 subjects will be enrolled in the study (refer to section 12.0).

A subset of subjects enrolled in this study will be used to meet the Post-Market Clinical Follow-Up (PMCF) requirement for CE mark. Once this subset of subjects is enrolled and followed for 12 months

## Clinical Investigational Plan

and have evaluable primary endpoint data at the 3-month follow-up visit, a report will be submitted indicating completion of this requirement. The primary endpoint analysis will be performed when 66 subjects have completed 12 months of follow-up and have evaluable primary endpoint data at the 3-month follow-up visit.

### 4.2.2 Estimated time needed to enroll this subject population

## 4.3 OBJECTIVES

### 4.3.1 Primary Objective

Demonstrate superiority of the directional lead DBS therapeutic window to the omnidirectional lead DBS therapeutic window.

### 4.3.2 Secondary Objective

Demonstrate non-inferiority of the directional lead DBS therapeutic window to the omnidirectional lead DBS therapeutic window and comparison of UPDRS part III motor examination scores at 3 and 6 months to evaluate therapeutic differences in omnidirectional vs directional stimulation.

## 4.4 ENDPOINTS

### 4.4.1 Primary Endpoint

The proportion of subjects for which at least one lead's therapeutic window (evaluated by a blinded evaluator) is greater using directional stimulation than omnidirectional stimulation, tested against a performance goal of 60%, at the 3-month follow-up visit. The directional segment with the widest therapeutic window will be compared to omnidirectional stimulation.

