### Clinical Investigational Plan

#### 1.0 SYNOPSIS

Title	Post Market Clinical Follow Up Evaluating the Infinity Deep Brain Stimulation Implantable Pulse Generator System
Acronym	PROGRESS
Purpose	The purpose of this post market study is to characterize the clinical performance of the Infinity Deep Brain Stimulation (DBS) Implantable Pulse Generator (IPG), DBS leads, extensions and related system components.
Primary Objective	Demonstrate superiority of the directional lead DBS therapeutic window to the omnidirectional lead DBS therapeutic window.
Secondary Objectives	Demonstrate non-inferiority of the directional lead DBS therapeutic window to the omnidirectional lead DBS therapeutic window and compare Unified Parkinson's disease Rating Scale (UPDRS part III motor examination) at 3 and 6 months to evaluate therapeutic differences in omnidirectional vs directional stimulation.
Primary Endpoint	The proportion of subjects for which at least one lead's therapeutic window (evaluated by a blinded evaluator) is greater using directional stimulation than omnidirectional stimulation, tested against a performance goal of 60% at the 3-month follow-up visit.
Secondary Endpoints	If primary endpoint not met, the proportion of subjects with a therapeutic window (evaluated by a blinded evaluator) which is larger under directional stimulation than omnidirectional stimulation tested against a performance goal of 40% at the 3 month follow-up visit; Comparison of 3-month vs. 6-month UPDRS part III motor examination scores (evaluated by a blinded evaluator) to assess therapeutic differences in omnidirectional vs. directional stimulation.

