## 4.0 STUDY DESIGN

### 4.1 PURPOSE

The purpose of this post market study is to characterize the clinical performance of the Infinity DBS system including IPG, leads, extensions and related system components.

The PMCF requirement for this study will be to demonstrate superiority of directional stimulation compared to omnidirectional stimulation, as measured by therapeutic window. The primary endpoint will be evaluated for the first 66 subjects who complete the 12-month follow-up visit and have evaluable primary endpoint at the 3-month follow-up visit.

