### 4.4.2 Secondary Endpoint

If primary endpoint not met, the proportion of subjects with a therapeutic window (evaluated by a blinded evaluator) which is larger under directional stimulation than omnidirectional stimulation tested against a performance goal of 40% at the 3 month follow-up visit; Comparison of 3-month vs. 6-month UPDRS part III motor examination scores (evaluated by a blinded evaluator) to assess omnidirectional vs. directional stimulation.

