## Clinical Investigational Plan

### 12.1.2 Secondary Endpoint

#### 12.1.2.1 Secondary Endpoint 1

If the primary study endpoint is not met, the following hypothesis will be tested to evaluate non-inferiority of therapeutic window with directional stimulation compared to omnidirectional stimulation.

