#### Hypothesis

The hypothesis is formally expressed as:

$$H_0: p \leq 0.40$$

$$H_a: p > 0.40$$

where  $p$  is the probability that the therapeutic window under directional stimulation is larger than the therapeutic window under omnidirectional stimulation (success).

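### Beating 60% on a widest-of-three, either-lead endpoint is a valid performance-goal result, but does not by itself show that the directional window is superior

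*Combined protocol and SAP*

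**What the plan says.** The primary objective (Sections 1.0 and 4.3.1) is to "Demonstrate superiority of the directional lead DBS therapeutic window to the omnidirectional lead DBS therapeutic window". Section 4.1 states the PMCF requirement in the same terms: to "demonstrate superiority of directional stimulation compared to omnidirectional stimulation, as measured by therapeutic window".

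The endpoint meant to show this is a proportion of subjects. Under Section 4.2 a subject succeeds "if one or both leads has a larger therapeutic window with directional stimulation than omnidirectional stimulation". For each lead, Sections 4.4.1 and 12.1.1 fix the directional value: "The directional segment with the widest therapeutic window will be compared to omnidirectional stimulation". Section 6.6 supplies the readings. Step 1 of directional testing takes segments A, B and C of one contact. An optional Step 2 adds up to three two-segment configurations. Omnidirectional testing takes one selected contact per lead.

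Section 12.1.1 tests the proportion against 60% with a one-sided 95% Clopper-Pearson lower bound. Section 12.2 assumes a 75% success rate; the rest of that paragraph is blacked out.

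If the primary test fails, Section 4.4.2 turns to a proportion "which is larger under directional stimulation than omnidirectional stimulation tested against a performance goal of 40% at the 3 month follow-up visit". Section 4.3.2 describes the aim as "Demonstrate non-inferiority of the directional lead DBS therapeutic window to the omnidirectional lead DBS therapeutic window", and Section 12.1.2.1 says "the following hypothesis will be tested to evaluate non-inferiority of therapeutic window with directional stimulation compared to omnidirectional stimulation".

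**The concern.** Two rounds of best-of selection favour the directional side: first over segments within a lead, then over the two leads. Reading error alone will therefore often make the widest of several directional readings exceed a single omnidirectional reading, even when no direction is truly better. A superiority claim at the 5% level has to hold in every no-benefit case, and equal true windows is one of them. If the no-difference success rate is above 60%, rejecting p ≤ 0.60 says nothing about whether the directional window is wider.

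The conclusion named as the primary objective and the PMCF requirement is at stake. Two gaps in definition add to the difficulty. The hypothesis in Section 12.1.1 defines p without the either-lead rule of Sections 1.0, 4.2 and 4.4.1, and so does Section 12.1.2.1. The endpoint refers to a segment, while Section 6.6 speaks of six assessments and makes three of them optional, so it is unclear whether two-segment tests count.

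**Working it through.** **Inputs from the documents.** Two leads per subject (Section 4.5.1, bilateral implant); three Step 1 segment readings and one omnidirectional reading per lead (Section 6.6); success is a strictly greater window, so a tie fails (Section 4.4.1); goals of 60% and 40%, 5% level, exact lower bound (Sections 12.1.1 and 12.1.2.1); 66 evaluable subjects (Sections 4.2.1 and 12.12); planning rate 75% (Section 12.2).

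**The plan's own rule.** With n = 66, 46 successes give a lower bound of 0.591 (fail) and 47 give 0.607 (pass). P(X ≥ 47 | p = 0.60) = 0.0395, so the test holds its level for the stated hypothesis. P(X ≥ 47 | p = 0.75) = 0.805. The power target is blacked out, so 66 cannot be formally reproduced, but it is consistent with 80%. For the 40% goal, 33 successes give 0.393 (fail) and 34 give 0.408 (pass); the size is 0.0383.

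**Success rate with equal true windows.** Assume that errors are exchangeable across configurations, that there are no ties, and that the leads are not negatively dependent.

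- Per lead: P(largest of k exceeds one other) = k/(k+1). For k = 3 this is 3/4.
- Per subject, fully dependent leads: 3/4 = 75%.
- Per subject, independent leads: 1 − (1/4)² = 15/16 = 93.75%.
- P(X ≥ 47) is 0.805 at 75% and above 0.999 at 93.75%.

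The lower end equals the planning rate, so under these conditions the no-benefit case passes at least as often as the planned alternative.

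**Number of readings.** If the two-segment tests count (k = 6), the range is 6/7 = 85.7% to 48/49 = 98.0%. If only two segments are tolerated (k = 2), it is 2/3 = 66.7% to 8/9 = 88.9%.

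**Ties and narrower segments.** The documents give no amplitude step, reading error or lead correlation. The figures below are simulations under assumptions: normal reading errors with SD 1, k = 3, the window rounded to a step expressed in SDs of reading error, and ties failing. They show direction and rough size only.

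| Assumed truth and step | P(pass 60% test), lead correlation 0 / 0.5 / 1 |
|---|---|
| Equal windows, no ties | >0.999 / >0.999 / 0.80 |
| Equal windows, step 1 SD | 0.998 / 0.91 / 0.05 |
| Equal windows, step 2 SD | 0.48 / 0.13 / <0.001 |
| Best segment equal, two narrower by 1 SD, no ties | 0.997 / 0.87 / 0.04 |
| Best segment equal, two narrower by 1 SD, step 1 SD | 0.41 / 0.07 / <0.001 |
| Every segment narrower by 0.5 SD, no ties | 0.998 / 0.91 / 0.05 |

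These values depend on the rounding model. Section 6.6 defines the window as a difference of two thresholds. Rounding each threshold separately raises the equal-window, 2 SD result to about 0.7 (independent leads) and 0.3 to 0.4 (correlation 0.5).

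**The 40% test, if scored the same way.** At a 75% rate, the chance of at least 34 successes exceeds 0.999. If every segment were truly narrower by 1 SD, with no ties, it would be 0.999 / 0.97 / 0.16 at lead correlation 0 / 0.5 / 1. No margin in window width is stated.

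**The case against.** The strongest reply is that the test is valid as written. The hypothesis concerns a proportion, the bound is exact, and the widest-segment and either-lead rules are openly stated. Comparing the best direction is how the lead would be used, and Section 2.0 cites a prior acute study that did so. Equal windows in every direction is the no-benefit case least like the background, which expects directions to differ. The omnidirectional contact is itself chosen for benefit from contacts 1 to 4, while directional testing is confined to contact 2 or 3, which plausibly favours omnidirectional. Section 12.3 also disclaims pass/fail criteria.

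Much of this stands. The exact test does control error for p ≤ 0.60, and best direction is a fair question. None of it turns p > 0.60 into a wider directional window, because equal windows remains a no-benefit case that a superiority claim must cover. The evaluator blind and the coin flip deal with observer and order bias, not with selecting and scoring on one reading. The comparison of mean windows in Section 4.4.3 is descriptive. Section 12.3 does not cancel the rejection rule in Section 12.1.1 or the requirement in Section 4.1.

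A reader might go further and infer that the study is bound to pass, that its real error rate is 80% or more, or that the 60% goal is unjustified. The documents support none of these. The high figures need equal windows and few or no ties; other assumptions give less than 5%. A rationale for 60% may lie in the blacked-out part of Section 12.2, so its absence cannot be held against the plan.

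**Conclusion.** The concern holds in this form: success against 60% is a valid performance-goal result for the best directional segment, but it does not by itself demonstrate superiority of the directional window. The 40% test likewise does not by itself demonstrate non-inferiority.

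The size is conditional. With equal windows, exchangeable errors, three readings per lead and no ties, success is 75% to 93.75% and the chance of passing is 0.80 to more than 0.999. With an assumed step of 2 SD it is about 0.5 for independent leads and about 0.13 at correlation 0.5, and in other cases it is below 5%. Confidence is high for the mechanism and the no-tie arithmetic. The documents do not show which case applies, so the true no-difference rate is unknown. Because the gap lies between the primary test and the primary claim, and closing it is cheap, the wording should be changed.

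**What to change.** 1. **One definition of success** in Sections 4.4.1, 4.4.2, 12.1.1 and 12.1.2.1, including both definitions of p: on at least one lead, the widest directional window tested exceeds the omnidirectional window at month 3, with ties counted as failures. State whether the optional two-segment tests count.

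2. **Keep both tests and change what they are called.** Report the 60% and 40% results as performance-goal results for the best directional segment, not as superiority or non-inferiority. Align Sections 1.0, 4.1, 4.3.1, 4.3.2 and 12.1.2.1. Beside the result, give the no-difference success rate with its assumptions: amplitude step, repeatability, lead correlation and number of tests.

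3. **Optional supportive analysis, clearly labelled.** Compare the contact and segment selected at month 3 with omnidirectional stimulation on fresh readings at the planned 12-month blinded-evaluator test, using one paired difference per subject. Fresh readings remove selection on reading error. State the limits: a different time point, subject blinding for the first 6 months only (Section 6.6), and possibly low power. If the sponsor wants to rest a superiority claim on this analysis, it needs a stated place in the testing order.

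**Cost.** Items 1 and 2 need no new visit, test or subject; the price is a weaker headline claim. Changing the PMCF wording in Section 4.1 may need outside agreement (an assumption). Item 3 requires the month-3 contact and segment to be retested at month 12, which the current text does not guarantee.

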### 4.4.2 Secondary Endpoint

If primary endpoint not met, the proportion of subjects with a therapeutic window (evaluated by a blinded evaluator) which is larger under directional stimulation than omnidirectional stimulation tested against a performance goal of 40% at the 3 month follow-up visit; Comparison of 3-month vs. 6-month UPDRS part III motor examination scores (evaluated by a blinded evaluator) to assess omnidirectional vs. directional stimulation.

### 4.4.3 Descriptive Endpoints

The following data will be collected:

Evaluation of subject and clinician stimulation preference at 6-month follow-up visit;

Change in therapeutic effectiveness measured by UPDRS part III motor examination at the 12-month follow-up visit from baseline visit;

Change in ADLs as determined from the UPDRS part II ADLs at the 3-, 6-, and 12-month follow-up visits from baseline visit;

Change in quality-of-life as measured by the PDQ-39 at the 3-, 6-, and 12-month follow-up visits from baseline visit;

Evaluation of device-related adverse events;

Evaluation of subject and programmer satisfaction with product usability at the 12-month follow-up visit.

Comparison of mean values of therapeutic window with directional and omnidirectional stimulation;

## Clinical Investigational Plan

Current (amplitude) at which first sustainable side effect is observed with directional and omnidirectional stimulation;  
Current (amplitude) at which first sustainable stimulation-induced side effect is observed with directional and omnidirectional stimulation;  
Minimum therapeutic current with directional and omnidirectional stimulation;  
Optimal therapeutic current with directional and omnidirectional stimulation;  
Total amount of time required for programming and each study visit.  
Long-term outcomes evaluated by change compared to baseline in UPDRS part III motor examination, UPDRS part II ADLs and PDQ-39, at the 36-month follow-up visit.

### 4.5 INCLUSION AND EXCLUSION CRITERIA

A subject who meets all of the inclusion criteria and none of the exclusion criteria is eligible to participate in this study.

All subjects enrolled in the clinical study (including those withdrawn from the clinical study or lost to follow-up) will be accounted for and documented, assigning an identification code linked to their names, alternative identification or contact information.

This log will be kept up to date throughout the clinical study by the principal investigator or an authorized designee. To ensure subject privacy and confidentiality of data, this log must be maintained throughout the clinical study at the clinical site.

To participate in this clinical subject, the subject must meet all of the following inclusion criteria:

#### 4.5.1 Inclusion Criteria

- 1) Subject is able to provide informed consent;
- 2) Subject is diagnosed with Parkinson's disease (PD) and has been recommended to receive an Infinity DBS system with a bilateral DBS implant in the Subthalamic Nucleus (STN), or has received an implant of an Infinity system with bilateral lead implants in the STN;
- 3) Subject must be available for follow-up visits.

A subject is not eligible for clinical study participation if the subject meets any of the following exclusion criteria:

#### 4.5.2 Exclusion Criteria

- 1) Subject is not a surgical candidate;
- 2) In the investigator's opinion, the subject is unable to tolerate multiple programming sessions within a single setting;
- 3) Subject is unable to comply with the follow-up schedule.

### 4.6 SUBJECT POPULATION

#### 4.6.1 Subject Screening

All subjects presenting at the investigational site can be screened by a member of the investigational team previously trained on the CIP and delegated to do so.

## Clinical Investigational Plan

Subjects who do not meet the inclusion/exclusion criteria will not be eligible to participate in this study.

Subjects meeting the inclusion/exclusion criteria will be fully informed about the study and asked to participate in the study. In case the subject agrees, a duly signed and dated Patient Informed Consent will be obtained.

### 4.6.2 Point of Enrollment

Subjects are considered enrolled in the study from the moment the subject has provided written Patient Informed Consent. (Refer to section 4.7 for the informed consent process). Although subjects exit the study after completion of the 12-month visit, subjects who provide written informed consent by signing the informed consent addendum for long-term follow-up may participate in 24- and 36-month follow-up visits. Follow-up visits will be scheduled based on date of initial programming.

### 4.6.3 Enrollment of Medicare Beneficiaries

In the United States, subjects enrolled in the clinical study are expected to be consistent with the Medicare population based on age and as such, the study results are expected to be generalizable to the Medicare population.

## 4.7 INFORMED CONSENT PROCESS

### 4.7.1 General process

Prior to enrolling in the clinical study and conducting study-specific procedures, all subjects will be required to provide informed consent, as required by applicable regulations and the center's EC or IRB. Informed consent must be obtained from each subject prior to any study-related procedures. The consent form must be signed and dated by the subject and by the person obtaining the consent.

The principal investigator or an authorized designee will conduct the informed consent process. This process will include a verbal discussion with the subject on all aspects of the clinical study that are relevant to the subject's decision to participate in the clinical study.

The subject shall be provided with the informed consent form that is written in a language that is understandable to the subject and has been approved by the center's EC or IRB. Failure to obtain informed consent from a subject prior to study enrollment should be reported to St. Jude Medical within 5 working days and to the reviewing center's EC or IRB consistent with the center's EC or IRB reporting requirements.

